CLINICAL STUDY PROTOCOL

The Facial nerve palsy And Cortisone Evaluation (FACE) study in children:

A randomized double-blind, placebo-controlled, multicenter trial

Development Phase

Sponsor Project No:	FACE-01
EudraCT number:	2017-004187-35
Investigational Product:	Prednisolone
Sponsor:	Dalarnas county council (Region Dalarna)
Sponsor Representative:	[name], research manager (Forskningsdirektör) Region Dalarna [name] Sweden [contact] [contact] E-mail address: [contact]
Coordinating Investigator	[name] [name], PhD Center for Clinical Research Dalarna (CKF) [name]

[name] Sweden [contact] [contact] E-mail address: [contact]

The clinical study will be conducted, and essential documentation archived, in compliance with the requirements of the ICH Guideline for Good Clinical Practice.

SYNOPSIS

Title of study:	
The Facial nerve palsy And Cortisone Evaluation (placebo-controlled, multicenter trial	(FACE) study in children: a randomized double-blind,
Name of Sponsor/Company: Dalarnas county council (Region Dalarna)	
Name of investigational product: Prednisolone	
Investigator(s) and study center(s):	
[name], coordinating investigator	
16-20 study centers with a principal investigator at e	each center (see separate document)
Planned study period: 2018-2024	Phase of development: Development Phase IV
Primary objective:	I
To evaluate the efficacy of cortisone versus placebo	o treatment in children with acute facial nerve palsy.
Secondary objective:	
	ompared to the total recovery rate at 12 months, in order to sible and/or useful in children with acute facial nerve palsy.
To evaluate subjective symptoms and influence in c	daily life in children with acute facial nerve palsy.
To evaluate the safety profile for cortisone in children	ren with acute facial nerve palsy.
Methodology: Randomized double-blind, placebo-controlled, m Number of subjects (planned): 500	ulticenter trial

SYNOPSIS

	1 117
	 1. 1-17 years of age Acute peripheral unilateral facial nerve palsy
	 Acute peripheral unilateral facial nerve palsy Less than 72 hours of duration of symptoms
	 Less that 72 hours of dutation of symptoms Signed informed consent
	T. Signed monited consent
clusi	on criteria:
1.	Head trauma < 1 month
2.	Central or bilateral facial nerve palsy
3.	Malformations in head and neck
4.	Conditions not compatible with cortisone treatment (hypertension, diabetes mellitus, psychiatric
	disorder, active or latent tuberculosis, intolerance of lactose)
5.	Current or past oncological diagnosis
6.	Other serious medical conditions (meningitis, encephalitis, stroke)
7.	Acute otitis media
	Signs of herpes simplex or varicella zoster infection (vesicles in the ear region)
9.	Pregnancy or breastfeeding
	Use of any systemic or inhaled steroids within 2 weeks prior onset of symptoms
	Immunization with live vaccine 1 month prior onset of symptoms
12.	Requirement of live vaccine within 2 months from start of experimental treatment (prednisolone or placebo)
13	Evaluation of primary endpoint at 12 not feasible for any reason
	Previously included into the FACE study
vestig	ational product, dosage and mode of administration:
edniso	olone capsules 5 mg, dosage 1 mg/kg body weight (maximum 50 mg) x 1, per oral
iratio	n of treatment:
days	
·	control, dosage and mode of administration:
	capsules, same number of capsules as investigational product for each child, maximum 10 capsules x 1,
r oral	capsules, same number of capsules as investigational product for each child, maximum 10 capsules x 1,
i oral	

SYNOPSIS

Primary Endpoint:

The total recovery rate at 12 months follow-up in the two treatment groups measured with the House-Brackmann scale.

Secondary Endpoints:

The total recovery rate at 12 months follow-up in the two treatment groups measured with the Sunnybrook scale.

The total recovery rate at 1 month follow-up as compared to the total recovery rate at 12 months follow-up, measured with Sunnybrook and House-Brackmann scale (prediction).

Quality of daily life at 1 and 12 months follow-up measured with the Facial Clinimetric Evaluation (FaCE) scale and the Facial Disability Index (FDI) and at the 12 months follow-up measured with the Synkinesis Assessment Questionnaire (SAQ).

Number of Adverse Events possibly or probably related to the study drug during the 12 months follow-up.

Statistical methods:

Intention-to-treat will be applied when analyzing results from the primary outcome.

Comparisons between groups for dichotomous endpoints (recovery/no recovery) will be performed using Fisher's exact test and for categorical endpoints (scale) using Mann-Whitney U-test. For correlations between scales, Pearson's correlation test, or Cohen's kappa if appropriate, will be used.

When predicting recovery at 1 month to 12 months, diagnostic performance will be calculated on total recovery defined as House-Brackmann grade 1.

Analysis of early predictors will be performed to understand variance of subgroups. Furthermore, logistic regression analysis will be used to evaluate recovery in relation to baseline data.

2 LIST OF ABBREVIATIONS AND DEFINITIONS OF TER
--

AE	Adverse Event
CIOMS	Council for International Organisation
	of Medical Sciences
CKF	Center for Clinical Research, Dalarna
CRF	Case Report Form
CV	Curriculum vitae
DSMB	Data safety monitoring board
DSUR	Development Safety Update Report
ENT	Ear Nose and Throat
ERB	Ethical Review Board
FACE	Facial nerve palsy and cortisone
	evaluation in children study
FaCE-scale	Facial Clinimetric Evaluation Scale
FDI	Facial Disability Index
GCP	Good Clinical Practice
ICF	Informed Consent Form
LSLV	Last subject last visit
MPA	Medical Products Agency
RCT	Randomized Controlled Trial
SAE	Serious Adverse Event
SAQ	Synkinesis Assesment Questionnaire
SUSAR	Suspected Unexpected Serious Adverse
	Reaction

5 BACKGROUND INFORMATION

The annual incidence of acute facial nerve palsy in European pediatric populations are about 5-21/100 000 children (1,2). The facial nerve palsy is often idiopathic, but may be caused by a *Borrelia* infection in the nervous system (2,3). The physiological reason for impairment of the facial nerve is an anatomically tight passage through the bone of the scull and when the nerve becomes swollen, for some reason, the nerve function is impaired and the facial muscles on the ipsilateral side are affected.

In children, *Borrelia* associated facial nerve palsy occurs more often (65%) than *idiopathic* facial nerve palsy (35%) (2). *Borrelia* associated facial nerve palsy is treated with antibiotics according to European guidelines (4,5).

An acute facial nerve palsy, regardless of etiology, may lead to a permanent dysfunction in 20-30 % of the patients, involving problems with tear secretion, drooling and pronunciation in addition to cosmetic and social problems (6-8).

Adult patients with idiopathic acute facial nerve palsy (Bell's palsy) are recommended cortisone treatment in order to improve the recovery rate (9). This recommendation is based on several randomized clinical trials (RCTs) (9,10). Studies on pediatric patients with acute facial nerve palsy and cortisone treatment are scarce and no RCT has been performed (11,12).

There are a few uncontrolled treatment studies on cortisone to children with acute idiopathic facial nerve palsy showing a total recovery rate up to 80-90% (13-16). Prednisolone in a dosage of 1-2 mg/kg daily in 7-14 days has been used in pediatric patients without reported adverse events (15,17).

One protocol has recently been published from New Zealand about a RCT study using prednisolone 1 mg/kg daily in 10 days (with a reduced dose day 7-10) for treatment of children with facial nerve palsy (18). We have in the FACE study chosen prednisolone in a dosage of 1 mg/kg daily in 10 days without taper in order to give a treatment that is easy to follow (compliance) and effective enough to regain function of the facial nerve (efficacy).

5.1 STUDY RATIONALE

Since no RCT has previously been performed on cortisone treatment in children with acute facial nerve palsy, there is a lack of evidence-based guidelines.

The aim of the FACE study is to evaluate the efficacy and safety of cortisone treatment given to children with acute facial nerve palsy in a randomized placebo-controlled trial.

If the cortisone treatment is shown to be beneficial for recovery in children with facial nerve palsy, cortisone treatment will be introduced in clinical practice and international evidence-based guidelines will be published.

5.2 STUDY TIME TABLE

Study planning 2017-2018.

Patient inclusion 2019-2023 with follow-up until 2024

Results and publishing 2025-2026

6 STUDY OBJECTIVES

6.1 PRIMARY OBJECTIVE

The primary objective of this study is to evaluate the efficacy of cortisone versus placebo treatment in children with acute facial nerve palsy.

6.2 SECONDARY OBJECTIVES

The secondary objectives are:

- to evaluate the total recovery rate at 1 month as compared to the total recovery rate at 12 months, in order to evaluate if prediction of recovery at 1 month is feasible and/or useful in children with acute facial nerve palsy
- to evaluate subjective symptoms and influence in daily life in children with acute facial nerve palsy
- to evaluate the safety profile for cortisone in children with acute facial nerve palsy

7 ENDPOINTS

7.1 PRIMARY ENDPOINT

The primary endpoint is the total recovery rate at 12 months follow-up in the two treatment groups measured with the House-Brackmann scale (19).

The House-Brackmann scale (1 is normal function and 6 is total loss of function) is chosen as primary outcome measure since it is a validated, objective instrument, easy to perform and most frequently used in previous studies (13,14,19). The time point 12 months for evaluation of total recovery is chosen as no further improvement of the facial nerve function is expected after 12 months (14).

7.2 SECONDARY ENDPOINTS

Secondary endpoints are:

• the total recovery rate at 12 months follow-up in the two treatment groups measured with the Sunnybrook scale (20, 21).

The Sunnybrook scale (100 is normal function and 0 is total loss of function) is another objective scale for grading the facial nerve function. It will be used as secondary outcome measure. It is validated for children, easy to perform and has been used in previous studies (20, 21). It correlates well to the House-Brackmann scale and has been shown to be useful for prediction of recovery in adult patients (21).

- the total recovery rate at 1 month follow-up as compared to the total recovery rate at 12 months follow-up, measured with Sunnybrook and House-Brackmann scale (prediction) (20, 21).
- quality of daily life at 1 and 12 months follow-up measured with the Facial Clinimetric Evaluation (FaCE) scale and the Facial Disability Index (FDI) and at the 12 months measured with the Synkinesis Assessment Questionnaire (SAQ) (22, 23).
- number of Adverse Events possibly or probably related to the study drug during the 12 months follow-up.

8 STUDY DESIGN

8.1 STUDY OUTLINE

The FACE study is a randomized double-blind, placebo-controlled, multicenter trial.

Efficacy of cortisone versus placebo treatment in children with acute facial nerve palsy will be measured by comparing the total recovery rate measured with the House-Brackmann scale at 12 months follow-up.

End of the study is defined as the 12 months follow-up visit for the last patient.

8.2 STUDY ASSESSMENTS AND PROCEDURES

A Principal Investigator (a pediatrician) at each study center will be responsible for clinical care of the patients.

The Principal Investigator (a pediatrician) or a co-Investigator (an Ear-Nose-Throat specialist) will be responsible for performing the objective evaluation of the facial nerve function on admission (or one day after) and at the follow-up visits 1 month and 12-months.

The Principal- and co-Investigators at each study center will be thoroughly informed how to assess the House-Brackmann and Sunnybrook scales in order to minimize inter-rater differences.

Study nurses will take care of parts of the study work, such as performing the one and two weeks telephone calls, collecting questionnaires from the child/parents/guardians, collecting and entering data in the CRFs and being the main contact person for the monitor.

Screening/Baseline visit

Children and their parents/guardians visiting the hospital for the child's acute facial nerve palsy will be informed about the study and eligibility criteria will be checked. If the child and the parents/guardians accept to participate in the study, an informed consent (ICF) will be signed by both parents/guardians. If only one parent/guardian is present at the visit, the other parent/guardian will be contacted by telephone, informed about the study, given the chance to ask questions and sent an ICF by email. The signed ICF will then be sent back by e-mail, or as a photocopy on the

mobile phone, to the investigator and saved in the Investigators file until the original ICF is returned.

Data about demographics, medical history, concomitant medication, physical examination including blood pressure will be collected. Blood sample for white and red blood cell count, CRP, electrolytes and glucose as well as investigation of the spinal fluid will be performed as part of normal clinical routine. The NeBoP score (a clinical neuroborreliosis prediction test), as used in routine, will be assessed on all children for early prediction of diagnosis associated to *Borrelia* infection (24).

Grading of the facial nerve palsy by using the House-Brackmann and Sunnybrook scales will be performed either by a pediatrician or an ear-nose-throat specialist (the principal or co-investigator).

The study medication including instructions about route of administration and dosage for the specific child will be distributed at the baseline visit. CRFs will be completed by the investigator or study nurse.

One week ±3 days telephone call and two weeks ±3 days telephone call

After one and two weeks, the study nurse will call the child and/or parents/guardians to follow up that study medication is taken according to instructions and to check whether any AEs have occurred. Bottles with remaining study medication will be returned after end of treatment for accountability check. Safety is followed-up by asking for AEs. CRFs will be completed by the study nurse.

One month ± 5 days and 12 months ±2 weeks follow-up visits

After 1 month and 12 months, the child with parents/guardians come to a follow-up at the pediatric or ENT-clinic. Grading of the facial nerve palsy with House-Brackmann and Sunnybrook will be performed. Safety followed-up by asking for adverse events. Also concomitant medications will be updated, if applicable. CRF's will be completed at 1 month and at 12 months by the investigator or study nurse.

The child and the parents/guardians will complete the Facial Clinimetric Evaluation (FaCE) scale, the Facial Disability Index (FDI) at 1 and 12 months follow-up and the Synkinesis Assessment Questionnaire (SAQ) at the 12 months follow-up.

Complementary treatment (for example physical therapy or massage) is asked for at the 12 months follow-up. If the patient has a moderate – severe persistent facial nerve palsy, a visit at an ENT-specialist will be arranged for further evaluation.

End of the study is defined as completed at the 12-months follow-up visit for the last included patient (LSLV). An end-of-the-study CRF for each participant will be completed by the Principal Investigator. The Medical Products Agency and the Regional Ethical Review Board will be informed within 90 days from the date of LSLV.

8.3 SCHEDULE OF EVENTS

	Screening/ Baseline	Telephone call 1 week ± 3 days	Telephone call 2 weeks ± 3 days	Visit 1 month ± 5 days	Visit 12 months ± 2 weeks
Informed consent	x				
Inclusion /Exclusion criteria	Х				
Medical history	Х				
Demographics	Х				
Weight/length/BMI	Х				
Physical examination	Х				
NeBoP score	Х				
House-Brackmann scale	Х			Х	Х
Sunnybrook scale	Х			Х	Х
Concomitant medication	Х			Х	Х
Distribution of study medication	Х				
Compliance of study medication		Х	Х		
Reporting of Adverse Events		Х	Х	Х	Х
Return of unused tablets				Х	
Facial disability index				Х	Х
Facial Clinimetric Evaluation Scale				Х	Х
Synkinesis Assessment Questionnaire					Х

9 SELECTION AND WITHDRAWAL OF SUBJECTS

9.1 SUBJECT INCLUSION CRITERIA

- 1. 1-17 years of age
- 2. Acute peripheral unilateral facial nerve palsy
- 3. Less than 72 hours since debut of symptoms
- 4. Signed informed consent

9.2 SUBJECT EXCLUSION CRITERIA

- 1. Head trauma < 1 month
- 2. Central or bilateral facial nerve palsy
- 3. Malformations in head and neck
- 4. Conditions not compatible with cortisone treatment (arterial hypertension, diabetes mellitus, psychiatric disorder, active or latent tuberculosis, intolerance of lactose)*
- 5. Current or past oncological diagnosis
- 6. Other serious medical conditions (meningitis, encephalitis, stroke)
- 7. Acute otitis media
- 8. Signs of herpes simplex or varicella zoster infection (vesicles in the ear region)
- 9. Pregnancy or breastfeeding
- 10. Use of any systemic or inhaled steroids within 2 weeks prior onset of symptoms
- 11. Immunization with live vaccine 1 month prior onset of symptoms
- 12. Requirement of live vaccine within 2 months from start of experimental treatment (prednisolone or placebo)
- 13. Evaluation of primary endpoint at 12 months not feasible for any reason
- 14. Previously included into the FACE study

*clarifications about some exclusion criterias:

Latent or active tuberculosis:

The Swedish children/adolescent population is at very low risk for TB. However, immigrants, children to immigrants and adopted children may be of higher risk and these groups are in Sweden routinely tested at the health check-up, including PPD (and if possible PPD, a Quantiferon test and lung X-ray) in order to find children in risk of having latent or active TB. Children diagnosed with latent or active TB are treated according to Swedish guidelines and will be excluded for participation in the study. If negative Quantiferon test, the TB diagnosis is excluded and the child can participate in the study.

Arterial hypertension:

All children diagnosed with arterial hypertension (with or without treatment) will be excluded. All other eligible children will be checked for blood pressure according to normal procedures at pediatric emergency wards or pediatric out-patients clinics before inclusion in the study. If the blood pressure (measured after relaxation in 5-10 minutes, in the right arm with the correct size of the cuff and with a mean value of three measurements) is above the 90th percentile (for age, sex and length) the child will be excluded for participation (27).

Children not being eligible for enrolment will be registered on the screening list for gender, age and reason for exclusion.

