10.6 CONCOMITANT THERAPY

Children with *Borrelia* associated acute facial nerve palsy will receive antibiotic treatment according to national guidelines, i.e. ceftriaxone 50-100 mg/kg x 1 in 10-14 days (1-7 years of age), or doxycycline 4 mg/kg x 1 in 10-14 days, or 200 mg x 1 first day and then 100 mg x 1 in 10-14 days (5).

If other concomitant medications permitted in the study are taken, they will be listed in the CRF. Data registered are generic/trade name, dosage, start and end date of the medication, and indication.

Use of any systemic or inhaled steroids within 2 weeks prior to onset of symptoms is not permitted. No live vaccines are permitted during the period one month prior to onset until 2 months after study treatment. For more information about medical conditions not permitted in the study, see Subject Exclusion Criteria, section 9.2.

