10.9 CONTINUATION OF TREATMENT

After 10 days treatment stops. No further treatment will replace the study medication.

Concomitant therapy (e.g. antibiotics 10-14 days, se 10.6) will be finished as prescribed by the responsible pediatrician.

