## 7. Definition of Analysis Populations

The analysis of data will be based on different subsets according to the purpose of the analysis.

Screening failure	Patients that have been screened but have not received any investigational product, will be considered as screen failures
Withdrawals	Patients that fulfil inclusion criteria and have signed informed consent but withdrew after inclusion (before data were collected)
Intention to treat (ITT)	All randomized patients receiving at least one dose of study drug and have available data. The ITT data set will be used for the safety as well as for the efficacy endpoints
Per Protocol (PP)	The PP comprises data from all subjects randomized and treated with evaluable efficacy data, and no major protocol deviation that significantly affects the evaluability of the subject in the study. The PP will be used for presentation of the primary endpoint only.

NOTE:

Screening failures will not be included in the study database.

For participants considered lost to follow-up, the CRF will be completed up to the last visit performed. Timing of withdrawal or loss to follow-up will be presented for each group and each time point in the CONSORT flow diagram.

Criteria for withdrawal are:

- AE that precludes further continuation of treatment
- No compliance with study procedures
- The patient becomes pregnant
- Other medical to the Investigator
- Patient's decision

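### The steroid exclusion window ends at symptom onset, so steroid given for the palsy between onset and randomisation does not exclude a child

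*Protocol*

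**What the plan says.** Protocol 9.2, criterion 10, excludes "Use of any systemic or inhaled steroids within 2 weeks prior onset of symptoms"; the synopsis has the same wording. Protocol 10.6 states the restriction again: "Use of any systemic or inhaled steroids within 2 weeks prior to onset of symptoms is not permitted". Both windows close at onset.

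Protocol 9.1, criterion 3, sets the time limit for entry: "Less than 72 hours since debut of symptoms". Up to three days can therefore pass between the end of the steroid window and inclusion.

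The sentence on vaccines in the same paragraph of 10.6 is built differently: "No live vaccines are permitted during the period one month prior to onset until 2 months after study treatment". That period runs straight through onset and randomisation.

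Other medication is recorded: "If other concomitant medications permitted in the study are taken, they will be listed in the CRF". The visit schedules in both documents place this at baseline, 1 month and 12 months. SAP section 7 limits the per-protocol set to children with "no major protocol deviation that significantly affects the evaluability of the subject in the study", and does not name non-study steroid as such a deviation. SAP section 8 plans no covariate adjustment.

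**The concern.** The hours between onset and inclusion are the ones in which a steroid would be started because of the palsy. Protocol section 5 says that adults with Bell's palsy "are recommended cortisone treatment in order to improve the recovery rate", and that uncontrolled studies have given cortisone to children. As written, a child who used an inhaled steroid ten days before onset is excluded, while a child given oral prednisolone for the palsy the day before screening is not. The second exposure is the trial drug, for the trial indication.

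If such children enter, some of those allocated to placebo have already had active drug, and some of those allocated to prednisolone receive more than the assigned course. The contrast between arms narrows. Because enrolling such a child complies with the criteria, it is not a protocol deviation, so the per-protocol analysis as defined would not remove the child either.

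**Working it through.** **1. Does any other rule close the gap?**
- The other 13 exclusion criteria: none concerns steroid started after onset.
- Withdrawal criteria (Protocol 9.3): none mentions it.
- Protocol 10.9: "After 10 days treatment stops. No further treatment will replace the study medication". This concerns the time after day 10, not the time before randomisation.
- Concomitant medication record: it makes use visible but excludes nobody.
- SAP 8.3: the 70% compliance threshold counts study capsules only.

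The gap stands. It concerns steroid use only; a child must still meet every other criterion.

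**2. The plan's own sample size.** Inputs from SAP section 9: recovery 80% (placebo) and 90% (prednisolone), two-sided 5%, power 80%, 430 evaluable, 10% not followed up, 500 enrolled (250 per arm).
- Exact Fisher power at 215 per arm is 80.3%, which matches 430.
- The normal approximation gives 2 × 199 = 398 without and 2 × 219 = 438 with continuity correction; the latter is within 3% of 430.
- 430 / 0.90 = 478, so 500 covers the stated loss.
- 500 × 0.90 = 450, or 225 evaluable per arm.

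**3. Dilution.** Let c be the share of placebo children given steroid between onset and randomisation, and f the fraction of the assumed 10-point effect that this exposure delivers. Neither is in the documents. Prednisolone recovery is held at 90%.

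Placebo recovery: p = 0.80 + 0.10 × f × c. Difference: d = 0.10 × (1 − f × c).

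Power = Φ{[d√n − 1.96 × √(2m(1 − m))] / √[p(1 − p) + 0.90 × 0.10]}, where m = (p + 0.90)/2.

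At c = 0 and n = 225: d√n = 0.10 × 15 = 1.5; m = 0.85; 1.96 × √0.255 = 0.990; √(0.16 + 0.09) = 0.5. Power = Φ(0.510/0.5) = Φ(1.02) = 84.6%.

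With f = 1, the upper bound for each c:

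| c | Placebo recovery | Difference (points) | Power, normal approx., 225 per arm | Power, Fisher exact, 225 per arm | Power, normal approx., 250 per arm |
|---|---|---|---|---|---|
| 0% | 80.0% | 10.0 | 84.6% | 82.1% | 88.2% |
| 5% | 80.5% | 9.5 | 81.3% | 78.3% | 85.2% |
| 10% | 81.0% | 9.0 | 77.6% | 74.2% | 81.7% |
| 20% | 82.0% | 8.0 | 68.7% | 64.6% | 73.3% |

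Fisher's exact test is the one named in Protocol 13.2; SAP 8.5 allows Chi2 or Fisher. Under Fisher, power is 80.6% at c = 2% and 78.3% at c = 5%, so it crosses 80% between them.

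**4. Partial effect.** Only the product f × c matters. At f = 0.5, c = 10% has the same power as the 5% row (81.3%), and c = 20% the same as the 10% row (77.6%). At f = 0.25, c = 20% also equals the 5% row (81.3%).

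**The case against.** The strongest case against is about size, and most of it stands.

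- **Likelihood.** Protocol 5.1 says evidence-based guidance for children is lacking, and Protocol 16.2 says no alternative treatment exists. Section 5 calls paediatric steroid studies scarce, limits the adult recommendation to idiopathic palsy, and puts 65% of childhood cases down to *Borrelia*, which is treated with antibiotics. This suggests that pre-treatment may be uncommon. Nothing in the documents shows that it happens, and the values of c have no source.
- **Exposure.** With under 72 hours available, a pre-treated child would have had one or a few daily doses. Full credit for a 10-day effect is generous.
- **Analysed number.** SAP 8.8 imputes missing primary outcomes, so up to 250 per arm may be analysed, and SAP section 9 raised 430 to 500 partly for uncertain assumptions. Both leave some margin, although imputation may itself dilute the difference.
- **Validity.** A reader might infer that the gap contaminates the placebo arm selectively or tilts the result towards prednisolone. The documents do not support that. The exposure precedes allocation, so it is a baseline characteristic expected to balance, and the randomised comparison stays valid.

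It can also be said that investigators would not enrol such a child. Nothing written tells them not to, and consistent practice across the 16–20 planned centres is what an eligibility criterion is for. So these arguments limit the consequence but do not close the gap.

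**Conclusion.** The gap in wording is certain; its effect is not. Followed exactly, the criteria admit a child already given the trial drug for this palsy. The consequence is dilution of the primary difference towards zero. On the normal approximation with 225 per arm, the upper-bound loss takes power from 85% to 81%, 78% and 69% at 5%, 10% and 20% pre-treatment. These figures rest on assumed rates, on a full 10-day effect from a few doses, and on no change in recovery in the prednisolone arm.

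A reader might conclude that the trial is underpowered. That does not follow: the documents give no rate, and at a low rate or a partial effect the loss is small. The reason to act is that the correction is specific and cheap.

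**What to change.** **Protocol.** Amend criterion 10, the synopsis and section 10.6 together, so that the steroid exclusion window runs without a break from 2 weeks before onset to randomisation. The live-vaccine restriction in 10.6 already covers that interval.

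**SAP.** For children already enrolled, use the baseline concomitant-medication record to identify those who received steroid between onset and randomisation, and add a sensitivity analysis of the primary endpoint without them. That status is fixed before allocation, so leaving them out keeps the comparison between randomised groups. The analysis depends on the baseline record having captured such use.

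Do not remove children from the per-protocol set for steroid given after randomisation unless the protocol first states such a rule. Neither document expressly prohibits non-study steroid during the 10-day course, so there is no rule to deviate from. Exclusion on post-randomisation treatment can also bias the set, since that treatment may depend on recovery and on arm.

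**Cost.** A signed amendment is needed, with notification of the Medical Products Agency and the Ethical Review Board for review and approval if the change is substantial (Protocol 20.1). A few children would no longer be eligible. Since inclusion is planned for 2019–2023, eligibility would be mixed before and after the change; the sensitivity analysis addresses that in part.
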